10.4 Withdrawal of Subjects

There is little evidence for side or adverse effects of the single dose LDX and GXR, hence withdrawal due to adverse effects is not expected. Nevertheless, potential adverse effects have been listed in the participant information sheet which will be provided to participants and their parents for their information. Participation will be discontinued if

- *the participant decides they no longer wish to continue*
- *recommended by the investigator*

Should a patient decide to withdraw from the study, the reason for withdrawal will be recorded as detailed as possible.

Participants who wish to withdraw from the study will be asked to confirm whether they are still willing to provide the study specific data at visits that were completed.

10.5 Expected Duration of Study.

1st May 2018 – 31st December 2020

Provided a timely reception of ethical approval we will begin recruitment in May and expect to begin testing the first participant by June 2018. We predict that we will be able to test one participant a month, depending on participant and scanner availability. We aim to finalise data collection by 31st December 2020 latest. Following that, we will begin data analysis, preparation of publications, and the PhD student will begin thesis write up.

11. Study Procedures

The following procedure will be followed in this study:

We will recruit 20 young people aged between 8 and 20 years with a current diagnosis of ADHD, who have never taken medication for ADHD (medication-naïve) or who have not been on ADHD medication for at least 3 months. All participants will have no history of substance abuse and no neurological deficits, learning disability, reading, speech, or language disorder, no other major clinical psychiatric disorder other than ADHD and autism, and no contraindications for LDX or GXR. These patients will be identified within SLAM and other clinics and will have already received a diagnosis of ADHD from a clinician or will be on a community waiting list awaiting clinical ADHD assessment. The family will be given a letter inviting the patient to participate as well as an information sheet.

If participants are interested in taking part their informed consent (or that of their parents where participants are under 16) will be sought and recorded by the PhD student. The PhD student will make sure that the participants have no contraindications to participation in this study (including MRI and drug related contraindications). Once they have agreed to participate in the study, we will invite parents and their child to come for a pre-assessment meeting at the Institute of Psychiatry, Psychology and Neuroscience where we will perform the following assessments:

- 1) Edinburgh Handedness Inventory (Oldfield, 1971)
- 2) IQ (WASI-II) (Wechsler et al., 1999)
- 3) Social Communication Questionnaire (Rutter et al., 2001)
- 4) Kiddie Schedule for Affective Disorders and Schizophrenia (K-SADS), ADHD module (Kaufman et al., 1996); this assessment will be audio-recorded for reliability purposes, consent will be sought
- 5) ADHD Rating Scale (ADHD-RS) to measure ADHD symptom severity (DuPaul et al., 1998)
- 6) The Conners-Third Edition: Parent Rating Scales, Short Form [Conner 3- P(S)] to assess ADHD severity (Conners, 2008)
- 7) ECG; this will be performed to ensure the participants have no cardiac contraindications to using LDX or GXR, the results will be reviewed by a doctor; patients who have a heart rate below 65 beats/minute will be excluded
- 8) Blood pressure; this will be measured in order to be able to exclude patients with systolic

blood pressure of < 90 mm Hg and diastolic blood pressure of > 90 mm Hg

9) Physical measurements (i.e. weight); this will be taken to accurately calculate the medication dosage

Additionally, the patient will be familiarised with the scanner environment by visiting the "mock scanner" and trained on the tasks he or she will later complete in the actual scanner. If eligible the patient will be invited to come back to the IoPPN to complete the three fMRI scans. Each patient will participate in three testing sessions performed at three separate visits one week apart. Each patient will receive a single typical clinical weight adjusted dose of GXR (0.05mg/kg, being rounded to the closest dose of 1mg, 2mg, or a maximum of 3mg GXR), LDX (30mg if below 30kg, 50mg if above 30kg body weight), and placebo (10mg Vitamin C) in one of the scans, in a randomised order. After approximately 3.5 hours and an hour prior to the scan the participant will complete a battery of the following neurocognitive tasks lasting approximately 40 minutes:

- 1) Go/No-go - 5 min, assessing the participant's ability to inhibit a motor response and selective attention (Rubia et al., 2007)
- 2) Interference inhibition (Simon task) - 5 min, involving a stimulus-response incompatibility effect. The task measures interference inhibition and selective attention. In this task, subjects have to execute a motor response according to iconic information and to inhibit the tendency to make an incorrect response that is triggered by an interfering, and predominant, spatial information (Rubia et al., 2007)
- 3) Continuous performance task - 8 min, measuring target detection, sustained attention, as well as selective attention (Rubia et al., 2007)
- 4) Time discrimination task - 5 min, measuring the participant's ability to discriminate between time intervals that differ by several hundreds of milliseconds (Rubia et al., 2007)
- 5) Vigilance task - 7 min, assessing vigilance on the detection of signals that are difficult to identify (Mackworth, 1948).

Subsequently, patients will be taken to the MRI suite to undergo a brain scan. Patients will be scanned 4.5 hours after drug administration (where drugs have shown to have maximum plasma concentration). The researcher at the scan (i.e. PhD student) will not know which tablet is given on each occasion. This has been designed this way to minimise bias. Medication details will be kept by the supervisor, and will be given to the parents after the three scans have taken place, and to the PhD student to group the data once all the subjects have been scanned.

In each scanning session, the participants will complete the following tasks that have shown to elicit underactivation in task-relevant regions in ADHD and to be modulated by MPH and ATX:

- 1) Working memory task (N-back task) - 6min, measuring 3 levels of working memory difficulty and will also assess the default mode network decrease with progressively increasing working memory (Cubillo et al., 2013, Chantiluke et al., 2014)
- 2) Tracking stop task - 9min, measuring motor response inhibition and error monitoring (Rubia et al., 2005, 2011; Cubillo et al., 2013)
- 3) Parametric sustained attention task - 12min, investigating the effects of increasing load on sustained attention on brain activation (Christakou et al., 2013, Murphy et al., 2015)
- 4) Resting state fMRI - 8min, measuring intrinsic connectivity networks associated with ADHD (default mode network, cognitive control network, dorsal and ventral attention,

saliency, and motor networks).

Total scanning time for each session will be approximately 60 minutes. The duration of testing for each subject will be 3 weeks.

Additionally, a group of 20 healthy age-matched controls will be recruited. Healthy controls will have no diagnosis of ADHD or other major psychiatric conditions, they will be psychoactive-medication free, have no history of substance abuse and no neurological deficits, learning disability, reading, speech, or language disorder. Healthy controls will be assessed using the following measures during their first visit at the IoPPN:

- 1) Edinburgh Handedness Inventory (Oldfield, 1971)
- 2) IQ (WASI-II) (Wechsler et al., 1999)
- 3) Social Communication Questionnaire (Rutter et al., 2001)
- 4) The Conners-Third Edition: Parent Rating Scales, Short Form [Conner 3- P(S)] to assess ADHD and other disorders (Conners, 2008)

Additionally, the participant will be familiarised with the scanner environment by visiting the "mock scanner" and trained on the tasks he or she will later complete in the actual scanner. If eligible the participant will be invited to come back to the IoPPN for a testing session that will involve the same cognitive and fMRI tasks as conducted with ADHD patients. The duration of testing for each healthy control will be one week or less.

12. Assessment of Safety

12.1 Specification, Timing and Recording of Safety Parameters.

MRI is considered safe and non-invasive and there are no reported side effects. However, there is a slight risk that the scanner is sometimes perceived as unpleasant and uncomfortable. The researchers will be sensitive to this possibility and will suspend testing sessions at the request of the participant or at the first signs of distress and discomfort. The participant will be informed that he or she is free to terminate the scanning session whenever they want to. Alerting mechanisms ensure easy communication and radiographers will constantly check that the participant is content to remain in the scanner.

Adolescents are sometimes anxious about the scanner. To familiarise them with this new environment they will participate in a "mock scan" in an inactive scanner beforehand and be trained on the tasks included in the study. They will also be able to tell in the first scan whether they are happy to be scanned 3 times. Every effort will be made to ensure that they do not feel anxious or claustrophobic. However, if they feel that the scanner is frightening to them, they will not have to participate. The same applies for adolescents who feel claustrophobic in the scanner.

The scanner is also noisy and this may be unpleasant for some children. We will, therefore, expose them to the noise beforehand in the mock scanner. If the children feel that they dislike the noise, they do not have to participate. Also, in order to minimize the discomfort of the noise, we will provide all participants with headphones that are specifically designed to reduce the noise level. This is standard procedure for all scanning subjects at the IoPPN.

Participants will be informed of the non-invasiveness and safety of the MRI scan.

Because we require 3 scanning sessions of 60 minutes of repeated scanning for this project, we decided to only scan older children, i.e. young people between 8 and 20 years. If the patients for whatever reason are not happy or do not tolerate the repeated scans and decide to drop-out of the research they are allowed to do so at any time.

During a research MRI scan, information is sometimes obtained about neurological abnormalities. This will be assessed by a clinical radiographer who will then inform the patient's GP about any unusual anomalies which appear to be a cause for concern. The participant's parent/guardian will then be informed about these by the GP.

Young people with ADHD included into the study will be medication naïve or not had medication for at least 3 months and they will have to wait to start their medication (if they are planning to have medication) until the end of the study. This may be inconvenient for some patients but we will only include participants who are prepared to do this. Furthermore, we will attempt to keep the length of the testing period for each patient to a minimum, by scanning participants with a minimum intervals (1 week) between scans. Taking medication for the first time is a sensitive issue but this study will be under the strict guidance of a clinician, i.e. a child psychiatrist ([name]) will be responsible for prescribing the medication and for discharging patients, the psychiatrist will also be on call on the day of each scan. The side effects (listed in the information sheet) may or may not be experienced by patients and this may be uncomfortable and/or distressing for both patient and parents. However, we expect that the majority of our participants will be recruited via clinics where they will be expecting to be prescribed medication for ADHD in the near future. This will mean they will most likely have had full and frank discussions about the advantages and disadvantages of medication with the clinician and will have thought carefully about this issue before being recruited for this study.

The medication will be overencapsulated for blinding. To make it easy for patients to ingest the capsules the smallest size was chosen after consultation with Maudsley Pharmacy.

The 3T MRI scanner, which is CE marked, will be used for functional neuroimaging protocol as well as the conventional structural neuroimaging protocol. One of the functional imaging protocols will involve the use of multi-echo scanning sequence. The multi-echo sequence will significantly improve the quality of the resting state data, as it will reduce motion, respiration, cardiac function, and other non-neuronal artefacts. The sequence will be applied to the resting state scan only as the resting state data is highly sensitive to such artefacts. The enhanced functional multi-echo neuroimaging protocol used in the Institute of Psychiatry Centre of Neuroimaging Studies includes minor modification of the conventional use of the CE marked scanner. A customised pulse sequence program (i.e. software) has been developed to allow enhanced functional multi-echo imaging on the General Electric Magnetic Resonance Imaging (MRI) scanner to be used for this study. As application of this sequence involves using the MRI scanner outside its CE marking, a formal risk assessment was undertaken in order to investigate the safety implications of the use of this sequence (and in particular any additional risks relative to the manufacturer provided version) and to ensure appropriate procedures were in place to manage such risks. No additional risks were identified, and the sequence can therefore be used with standard precautions. Since its implementation, the sequence has been successfully applied in studies involving human participants

12.2 Procedures for Recording and Reporting Adverse Events

While there are side effects associated with long-term use of LDX and GXR, the single dose administration is unlikely to cause side effects. Nonetheless, any adverse effects will be monitored with a standardised parental questionnaire developed by Hill and Taylor (2001), extended to include GXR and LDX related side effects. Furthermore, a clinician will be on call for the scanning day in the unlikely case of any adverse effects. Moreover, potential side effects associated with the drugs (such as: drowsiness, headache, dizziness, dry mouth, fatigue, gastrointestinal problems, loss of appetite, palpitation, elevated blood pressure,

muscle spasm, euphoric mood) have been included in the information sheets for patient's and their parents' information.

In case of any serious adverse events (SAE) standard HRA reporting procedures will be followed. Related and/or unexpected SAE will be reported to the relevant Research Ethics Committee within 15 days of the Chief Investigator becoming aware of the event. All other safety reporting, including progress reports, declaration of conclusion, and summary of final report, will be performed according to the HRA guidelines.

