7.3 Study Flowchart

For ADHD patients:

	Pre-assessment	Visit 1	Visit 2	Visit 3
Date				
Start / End time				
Researcher Administered				
Eligibility checklist				
K-SADS (P/C)				
Self-Administered				
Background Information (P)				
Edinburgh Handedness (C)				
SCQ (P)				
CPRS (P)				
ADHD-RS (P)				
Adverse Effects Scale (P)				
Neurocognitive Measures				

WASI (30-40min)				
Go/No-go task (5min)				
Interference inhibition (Simon) (5min)				
Continuous performance task (8min)				
Time discrimination task (5min)				
Vigilance task (7min)				
fMRI Working Memory task (6min)				
fMRI Tracking Stop task (9min)				
fMRI Sustained Attention task (12min)				
fMRI Resting State (8min)				
Forms				
Consent form child				
Consent form parent				
MRI safety form				
MRI request form				
Receipt of payment				

Each session of cognitive tasks will consist of the below:

Go/No-go (5min)	Interference inhibition (Simon task; 5min)	Continuous Performance (8min)	Time Discrimination (5min)	Vigilance (7min)
-----------------	--	-------------------------------	----------------------------	------------------

Each MRI scan will consist of the below:

Structural Scan (10min)	fMRI Working Memory (N-back; 6min)	fMRI Tracking Stop Task (9min)	fMRI Parametric Sustained Attention (12min)	fMRI Resting State (8min)
-------------------------	------------------------------------	--------------------------------	---	---------------------------

Figure 1. Schematic overview of the design of the study. ADHD-RS, Attention Deficit Hyperactivity Disorder-Rating Scale; AES, Adverse Effects Scale; BP, Blood Pressure; CPRS, Conners' Parent Rating Scale; ECG, Electrocardiogram; EH, Edinburgh Handedness; K-SADS, Kiddie-Schedule for Affective Disorders and Schizophrenia; Neurocog. Battery, Neurocognitive Battery of tasks; SCQ, Social Communication Questionnaire; WASI, Wechsler Abbreviated Scale of Intelligence.

[figure not shown]
For healthy controls:

	Pre-assessment	Visit 1
Date		
Start / End time		

Researcher Administered		
Eligibility checklist		
Self-Administered		
Background Information (P)		
Edinburgh Handedness (C)		
SCQ (P)		
CPRS (P)		
Neurocognitive Measures		
WASI (30-40min)		
Go/No-go task (5min)		
Interference inhibition (Simon) (5min)		
Continuous performance task (8min)		
Time discrimination task (5min)		
Vigilance task (7min)		
fMRI Working Memory task (6min)		
fMRI Tracking Stop task (9min)		
fMRI Sustained Attention task (12min)		
fMRI Resting State (8min)		
Forms		

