10.1 Inclusion Criteria

Twenty young people with ADHD, 8-20 years old, medication-naïve or medication free for at least three months, recruited from local clinics, meeting DSM-5 criteria for ADHD using ADHD Diagnostic Interview and rating scales.

- Age range: 8-20 years
- Medication-naïve or on non-medicated for at least 3 months
- Meeting DSM-5 diagnosis of ADHD
- Score above clinical cut-off on the ADHD module of the Kiddie Schedule for Affective Disorders and Schizophrenia (K-SADS) (Kaufman et al., 1996)
- Score above clinical cut-off for ADHD on the short forms of the Conners Parent Rating Scales, CPRS (Conners et al., 2008)
- Score above cut-off on the ADHD Rating Scale, ADHD-RS (DuPaul, et al., 1998)
- IQ > 70 as tested on the WASI-II (Wechsler et al., 1999)

Mood and depression symptoms, autism, phobias, anxiety, conduct disorder, oppositional defiant disorder, and eating disorders will be allowed.

Twenty healthy young people, 8-20 years old, will be recruited.

- Age range: 8-20 years
- Not using psychoactive medications
- Score below cut-off for ASD on the Social Communication Questionnaire (SCQ) (Rutter et al., 2001)
- Score below cut-off for ADHD or other disorders on the short forms of the Conners Parent Rating Scales, CPRS (Conners et al., 2008)
- IQ > 70 as tested on the WASI-II (Wechsler et al., 1999)

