10.2 Exclusion Criteria

Exclusion criteria for ADHD participants:

- IQ < 70 (Wechsler et al., 1999)
- Currently on ADHD medication or has been on ADHD medication in the past 3 months
- Comorbidity with schizophrenia, bipolar disorder, learning disability, OCD, severe depression with current suicidal behaviour (as assessed by a clinical interview)
- Neurological problems, i.e. a history of severe neurological illness, e.g. brain tumour, epilepsy or a history of symptomatic seizures, polyneuropathy etc.
- Substance abuse history
- Other illness (cardiovascular, renal, hepatic, metabolic) that would impact the data integrity or safety of the subject (i.e. contraindicated to any of the treatments) as determined by the investigators

- Contraindication to MRI. i.e., previous implantation of metallic material, pacemaker, implanted medication pumps, neural stimulators, claustrophobia
- Unable to give informed assent or consent in the case of the parent
- Contraindications for LDX and GXR use (i.e. advanced arteriosclerosis, agitated states, hyperexcitability, hyperthyroidism, moderate or severe hypertension, symptomatic cardiovascular disease, heart rate < 65 beats/minute, systolic blood pressure < 90 mm Hg, diastolic blood pressure > 90 mm Hg)

Exclusion criteria for healthy controls:

- IQ < 70 (Wechsler et al., 1999)
- Currently on psychoactive medication treatment
- Diagnosis of a mental health disorder
- Scoring high on the questionnaires for ADHD (CPRS) or Autism (SCQ)
- Neurological problems, i.e. a history of severe neurological illness, e.g. brain tumour, epilepsy or a history of symptomatic seizures, polyneuropathy etc.
- Substance abuse history
- Other illness (cardiovascular, renal, hepatic, metabolic) that would impact the data integrity or safety of the subject (i.e. contraindicated to any of the treatments) as determined by the investigators
- Contraindication to MRI. i.e., previous implantation of metallic material, pacemaker, implanted medication pumps, neural stimulators, claustrophobia
- Unable to give informed assent or consent in the case of the parent

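### Participants may be up to 20 years old, but the only named adverse-effect instrument is completed by a parent, so mainly felt symptoms risk being missed, especially in older patients

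*Combined protocol and SAP*

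**What the plan says.** The inclusion criteria in section 10.1 set the same limits for patients and controls: "Age range: 8-20 years". Section 12.2 says that "any adverse effects will be monitored with a standardised parental questionnaire", based on a published scale that the team extended to cover the two study drugs. The patient flowchart in section 7.3 lists it as "Adverse Effects Scale (P", where P most naturally stands for parent. No other adverse-effect form is named.

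Section 12.2 adds that "a clinician will be on call for the scanning day in the unlikely case of any adverse effects". Sections 9 and 12.1 add that a psychiatrist attends at the end of the session and is responsible for discharge. Serious events follow a separate reporting procedure.

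On consent, section 11 seeks the participant's "informed consent (or that of their parents where participants are under 16". The exclusion lists in section 10.2 contain, for both groups, "Unable to give informed assent or consent in the case of the parent", with no age attached. On incidental MRI findings, section 12.1 sends the result to the GP and then states: "The participant's parent/guardian will then be informed about these by the GP". No age distinction is made there either.

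**The concern.** The age range takes in people who, under section 11, consent for themselves, and some who are adults. The safety questionnaire, the wording of the consent exclusion and the disclosure route are all written as if every participant were a child with a parent as spokesperson.

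For the questionnaire this matters because several of the effects listed in section 12.2 are experienced by the patient and become known to a parent only if the patient mentions them. A 19-year-old is less likely than a 9-year-old to be closely observed. That is a general expectation and is not taken from the documents. What is at stake is the completeness of the routine tolerability record after each dose. The BOLD and task-performance endpoints are not affected.

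**Working it through.** The plan states no figure on this point, so the check is mainly a comparison of sections, with one small calculation to size the group concerned.

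**1. Is the instrument really parent-only?** The flowchart gives no key, so P and C are read as parent and child by inference. It does vary the label: handedness is marked C, the K-SADS P/C, and the Adverse Effects Scale P alone. Section 12.2 agrees with that reading. The cells showing when the scale is given were lost in text extraction, so nothing is concluded about its timing.

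**2. Which listed effects are mainly felt?** Section 12.2 names 11: drowsiness, headache, dizziness, dry mouth, fatigue, gastrointestinal problems, loss of appetite, palpitation, elevated blood pressure, muscle spasm and euphoric mood. The documents do not classify them; on my own reading, headache, dizziness, dry mouth and palpitation (4 of 11) are clearly felt more than seen, and fatigue is arguably a fifth. Drowsiness, appetite loss and euphoric mood can be both felt and observed.

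**3. Do the other routes fill the gap?** The scan starts 4.5 hours after dosing and lasts about 60 minutes, so it ends about 4.5 + 1 = 5.5 hours after the dose. Section 8.2 gives half-lives of about 17 hours (GXR) and 9 hours (LDX), so drug is still present when the patient leaves. The psychiatrist can hear symptoms directly at that point and is on call for the day. However, no structured enquiry to the patient and no form for non-serious symptoms is described.

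**4. How many patients could be concerned?** Ages 8 to 20 inclusive are 13 single years. Assuming an even spread, which nothing in the documents supports or contradicts:
- Ages 16 to 20: 5/13 = 38%; 20 × 5/13 = 7.7 patients.
- Ages 18 to 20: 3/13 = 23%; 20 × 3/13 = 4.6 patients.
- Chance of at least one patient aged 18 to 20: 1 − (10/13)^20 = 99.5%.

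Without that assumption the number could be anything from 0 to 20.

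**5. Consent.** Take a participant aged 16 or over who consents but has no consenting parent. Section 11 admits that person. Section 10.2, read literally, excludes them. Below 16, or where a parent also consents, the two sections give the same result.

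**The case against.** The strongest reply is that no under-recording has been shown. The documents contain no reporting rates by informant or by age, and the questionnaire itself is not reproduced, so parents may be told to ask the patient. Patients spend hours with study staff, sessions are suspended at signs of distress, and a psychiatrist is at hand. Parents are blinded, and the same form is the only one named for all three conditions, so no bias between treatments is evident. Tolerability is not an endpoint. All of this stands. It lowers the weight of the point, but it does not supply a self-report or a record of symptoms told to the clinician.

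On consent, the exclusion in section 10.2 can be read as requiring parental consent only where it applies, and section 11 has the explicit age rule. Consent pages were removed before review, so age-specific forms cannot be called absent. This is an ambiguity more than a flat contradiction, but a researcher working from the exclusion list alone could turn away someone whom section 11 admits.

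A reader might go further and infer that eligibility as a whole rests on parents and varies with the section followed, because entry requires "Score above clinical cut-off for ADHD on the short forms of the Conners Parent Rating Scales, CPRS" and the ADHD-RS is also marked P. The documents do not support that. Patients also need a DSM-5 diagnosis and the K-SADS, which is marked for parent and child. The parent scales are required consistently throughout, so they create no conflict between sections.

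**Conclusion.** The point holds as a risk and as an inexpensive improvement. The only standardised adverse-effect instrument named is parent-completed, for patients up to 20, and mainly felt symptoms may go unrecorded. The size of any loss cannot be computed. The figures of about 8 and about 5 of 20 patients describe only how many might be in the older age bands under an even age spread.

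Two stronger statements are tempting. One is that adverse effects are in fact under-recorded in older patients; nothing in the documents measures this. The other is that a parent would be absent when symptoms appear after the visit; the documents do not show when the scale is completed or who is with the patient.

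The consent ambiguity is secondary. It affects only participants aged 16 or over without parental consent, on the literal reading of section 10.2. The incidental-findings route is a separate small gap: no direct route is stated to a participant who gave their own consent.

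**What to change.** - **Sections 7.3 and 12.2:** have the patient complete the existing Adverse Effects Scale alongside the parent at each dosing visit. Report both informants' answers, or state in advance which is primary for participants who consent for themselves.
- **Sections 10.2 and 11:** reconcile the wording on parental consent from age 16, so that both give the same answer for a participant who consents without a parent.
- **Section 12.1:** include the participant in the route for incidental MRI findings where the participant gave their own consent.

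The cost is amendment wording and at most 20 × 3 = 60 extra short forms, a few minutes each. The drawback is that parent and patient may disagree, which is why the reporting rule should be fixed before unblinding. No extra staff are needed.
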